NEW Tx is a flexible modular treatment such that modules are selected based on the needs of the individual to increase its generalizability across patients, settings, and providers as well as its acceptability to patients. The three modules of the intervention are as follows:

A. Nutrition/Weight Loss Module

To enhance nutrition, we review nutritious foods (e.g., high in vitamins and minerals, low in fat) in each of the food groups as well as teach participants how to calculate serving size to enhance portion control. We discuss the importance of a “balanced diet” as well as having essential vitamins and minerals, particularly ones that may be beneficial for mood disorders. Finally, we review food that may be unhealthy and why. Weight loss is tracked as needed and food diaries are used as needed (at minimum at baseline, week 10, and week 20) to monitor participants’ daily foods consumed and calories. Participants, with guide from their NEW Tx therapist, will determine a daily goal for caloric intake to assist in identifying healthy and realistic weekly weight loss goal. We utilize Cognitive Behavioral Therapy (CBT) strategies to challenge negative thoughts about changing food choices⁴⁴. We also include a session on emotional eating, or eating to cope with negative affect, by evaluating the accuracy of thoughts associated with the craving. We discuss positive coping strategies, or distraction activities, to replace food as a way to improve mood or “comfort” oneself. We also utilize the philosophy from Brownell’s LEARN program⁴⁵ that there are no “forbidden foods” as evidence suggests that this may increase cravings for these foods as well as negative thoughts about the module⁴⁶. We use psychoeducational materials to enhance adherence. We specifically discuss the impact of “psychological factors” and review research studies of diet programs that have had positive outcomes in severe mental illness. Finally, we employ behavioral strategies in NEW Tx, such as positive reinforcement, to enhance adherence through the use of reward charts. We then collaboratively set homework and weekly goals each session.

B. Exercise Module

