- ii. **Phase II:** In this phase, we will pilot test the NEW Tx methods compared to TAU ($n = 60$) to further examine feasibility, to estimate an effect size, and to explore its efficacy for reducing medical burden. TAU will be the control group in the Phase II pilot study as it is the standard treatment in the Massachusetts General Hospital (MGH) Bipolar Clinic and Research Program. Participants randomized to TAU who complete the first 20 weeks of the study will have the option to receive NEW Tx. TAU participants who chose to receive NEW Tx (the waitlist group) will follow the same procedures as the NEW Tx group over an additional 20 weeks such that they will have assessments at Weeks 30, (mid-treatment), 40 (post-treatment), and 52 (follow-up) (see Table 2). For TAU, medication and dosage changes are allowed as long as the change is recommended based on the guidelines and participants remain on a mood stabilizer. Medication changes will be monitored with the Clinical Monitoring Form Medication Module. All participants will have a three-month follow-up visit during which post-treatment measures and assessments will be repeated. Participants will be recruited with the same criteria as the nonrandomized trial, but will be randomized using a 1:1 allocation ratio with a blocking strategy. The assessments will be similar to those used in Phase I. In addition to the study staff utilized in Phase I, clinicians with training in CBT and mood disorders will be added as NEW Tx therapists.

B. Participant Selection and Recruitment

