Participants ($n = 6$ for the open trial phase; $n = 60$ for the randomized phase) will be recruited from within as well as outside the MGH Bipolar Clinic and Research Program, and we plan to recruit 1 participant per month for the Phase I open trial and 2 participants per month for the Phase II randomized trial. Some subjects will be self-referred, whereas others will be referred by MGH or community clinicians. Some subjects may be obtained from media advertisements. Potential participants will not be identified through medical records, and the researchers will not contact potential participants without their permission. If a clinician feels that one of his or her patients would be potentially appropriate for this study, the patient will be encouraged to contact the PI or the research assistant directly. Alternatively, the clinician may ask the patient to give permission to be contacted over the phone by either the PI or the research assistant. Written IRB approved informed consent will be obtained from all patients before protocol-specified procedures are carried out.

Patients may be referred to the study by their treating clinicians in the MGH Bipolar Clinic and Research Program, and will be recruited according to the following criteria:

i. **Inclusion Criteria**

- Diagnosis of Bipolar Disorder (Type I or II), which is the primary focus of treatment
- Ability to give informed consent
- Currently ill (CGI-BP ≥ 3)
- Age > 18 years and < 65 years
- Overweight individuals (BMI > 25); those with BMI of 25-30 must also have high rate of percentage of body fat (greater than or equal to 32% for women and 25% for men)

ii. **Exclusion Criteria**

- Unwilling/unable to comply with study procedures
- Endorsed item, confirmed by patient's physician, on the PAR-Q
- Euthymic (CGI-BP < 3)
- Diagnosis of anorexia nervosa or bulimia nervosa in the past month
- Diagnosis of substance dependence in the past month
- Active suicidality (MADRS item 9 score > 4)
- Pregnant (as analyzed by a urine pregnancy test)
- Exercising regularly (i.e., 5 days per week for 30 min)
- Neurologic disorder or history of head trauma
- Contraindications to exercise or diet interventions (e.g., co-morbid nutritional and metabolic diseases, physical injuries)

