- xv. **Post-Treatment Questionnaire** is an open-ended, 3 question measure that asks participants to identify aspects of the treatment that were helpful or not helpful and that could be improved.
- xvi. **Intent to Attend⁷²** is a single item that measures participants' intent to attend the next study visit which will be used in part to inform the extent to which attrition is ignorable⁷³.
- xvii. **DXA scans** measure total body composition and fat content using low-dose x-rays.
- xviii. **University of Rhode Island Change Assessment Scale (URICA)** is a 32-item, self-administered measure that is a reliable and valid measure of motivation and intention to change at entrance to treatment.
- xix. **Metabolic Cart Assessment**—Metabolic Cart Assessment—A metabolic cart is an electronic medical tool that is used to measure basal metabolic rate and can be used by medical professionals to determine someone's overall health condition. This test indirectly measures how much energy a person's body uses at rest by measuring the amount of oxygen a person consumes versus the amount of carbon dioxide a person expends.

Table 1. Schedule of Assessments for the NEW Tx and TAU groups

Weeks	0	1	2	3	4	5	6	7	8	9	10	11	12	13	14	16	18	20	32
	Pre										Mid							Post/ET	Follow-Up
MINI	x																		
Medical Hx	x																		
Psychiatric Hx	x																		
Demographics	x																		
PAR-Q	x																		
CGI-BP	x										x							x	x
Blood Draw**	x										x							x	x
Vitals	x									x							x	x	
DXA scan	x																x		
CMF	x									x							x	x	
MADRS	x									x							x	x	
YMRS	x									x							x	x	
LIFE-RIFT	x									x							x	x	
NEW Tx Scale																	x	x	
CEQ	x																		
CSQ-8																	x	x	
URICA	x																x	x	
Met Cart	x																x		
Post-Tx Questionnaire																	x	x	

EQ	x	x	x	x	x	x	x	x	x	x	x	x	x	x	x	x	x	x	x	x	x
Intent-to-Attend†	x	x	x	x	x	x	x	x	x	x	x	x	x	x	x	x	x	x	x	x	
Food Diaries†	x	x ¹	x	x ¹	x	x ¹	x	x ¹													

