ET= Early Termination. Vitals = Height (at Week 0 and Week 20), weight, waist circumference, blood pressure, pulse, and Dual X-Ray Absorptiometry (i.e., body composition). ** Includes lipid profile (i.e., cholesterol, triglycerides), metabolic panel (i.e., blood urea nitrogen (BUN), creatinine (Cr), electrolytes, blood glucose level), complete blood count (CBC), and thyroid stimulating hormone (TSH). C reactive protein (CRP) and inflammatory marker panels (Human TH1/TH2 10-Plex (IFN-g, IL-1b, IL-2, IL-4, IL-5, IL-8, IL-10, IL-12p70, IL-13, TNF-a)) will be included at pre- and post-treatment visits. A urine pregnancy test will be administered at Week 0 to determine eligibility. An EKG will be completed at Week 0 for participants \geq 40-years-old, if clinically indicated.

¹As needed.

†For the TAU group, will only be collected at Weeks 0, 10, and 20

Table 2. Schedule of Assessments for the Waitlist Group (TAU participants who choose to receive NEW Tx)Weeks	21	22	23	24	25	26	27	28	29	30	31	32	33	34	35	36	37	38	39	40	52
										Mid-tx									Post-tx	Follo w-up	
CGI-BP										x									x	x	
Blood Draw**										x									x	x	
Vitals										x									x		
DXA scan																			x		
CMF										x									x	x	
MADRS										x									x	x	
YMRS										x									x	x	
LIFE-RIFT										x									x	x	
NEW Tx Scale																			x	x	
CSQ-8																			x	x	
URICA	x																		x	x	
Met Cart	x																		x		
Post-Tx Questionnaire																			x	x	
EQ	x	x	x	x	x	x	x	x	x	x	x	x	x	x	x	x	x	x	x	x	
Intent-to-Attend	x	x	x	x	x	x	x	x	x	x	x	x	x	x	x	x	x	x	x	x	
Food Diaries	x ¹																				

ET= Early Termination. Vitals = weight, waist circumference, blood pressure, pulse, and Dual X-Ray Absorptiometry (i.e., body composition). ** Includes lipid profile (i.e., cholesterol, triglycerides), metabolic panel (i.e., blood urea nitrogen (BUN), creatinine (Cr), electrolytes, blood glucose level), complete blood count (CBC), and thyroid stimulating hormone (TSH). C reactive protein (CRP) and inflammatory marker panels (Human TH1/TH2 10-Plex (IFN-g, IL-1b, IL-2, IL-4, IL-5, IL-8, IL-10, IL-12p70, IL-13, TNF-a)) will be included at pre- and post-treatment visits. A urine pregnancy test will be administered at Week 0 to determine eligibility.

¹As needed.

D. Independent Evaluator Training

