There is a possibility that study patients will not improve from this treatment. During the study assessments, subjects may also experience some discomfort from discussing personal material and completing self-report questionnaires. Subjects may also experience some discomfort from the blood draw. Participants will be exposed to radiation from two DXA scans. The total amount of radiation exposure is equal to a whole body exposure of approximately 16 microSieverts. A microSievert is a unit of radiation dose. This amount of radiation is about the same as you would normally receive in 2 days from natural background sources from the earth and the sky. Participants will also participate in a metabolic cart assessment, in which a clear plastic canopy will then be fitted over the head and upper chest of the participants to collect the air the participant exhales for 15 minutes. Participants may experience some discomfort or anxiety.

There is a risk of breach of confidentiality and loss of privacy, which great care will be taken to prevent.

B. Protection Against Risks

We will take precautions to ensure that potential risks are minimized. All treatments will be provided by at least master-level mental health professionals with experience in CBT and mood disorders. NEW Tx therapists will be closely supervised by the PI. In the case of an emergency, the NEW Tx therapist will page the PI. If the PI is unavailable, the covering clinician will be paged. If immediate assistance is required, the participant will be directed to call 911 or go to the MGH Acute Psychiatric Service. The following procedures will also ensure participant safety:

- i. All participants who fail to respond to treatment or withdraw prematurely will be referred for alternative treatment. If withdrawal from the study is necessary, we will provide appropriate referrals for other treatment. The PI, or the covering clinician, will be available to discuss the study, alternative treatments, or any concerns about the study with subjects if requested by the participant, therapist, or independent evaluator.

- ii. Ratings on the MADRS suicide item will be monitored during the open trial (Phase I) and the randomized trial (Phase II). Participants' with a suicidality score greater than 4 at Week 0—for either trial—will be excluded from the study.

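### The waitlist group's third DXA scan is missing from the stated radiation exposure, and its pregnancy test is dated to a week that its schedule does not contain

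*Combined protocol and SAP*

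**What the plan says.** **Radiation.** Section VI.A (Potential Risks to Subjects) states "Participants will be exposed to radiation from two DXA scans". It puts the total at about 16 microSv and compares this with 2 days of natural background.

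**Schedules.** The table headed "Table 1. Schedule of Assessments for the NEW Tx and TAU groups" has two marks in its DXA row. Table 2, for TAU patients who later choose NEW Tx, has one DXA mark, in the post-treatment column. Section IV.A (Phase II) sets up that group: "Participants randomized to TAU who complete the first 20 weeks of the study will have the option to receive NEW Tx". It adds that these patients "will follow the same procedures as the NEW Tx group over an additional 20 weeks", and explains this by saying that "they will have assessments at Weeks 30, (mid-treatment), 40 (post-treatment), and 52 (follow-up".

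**Pregnancy.** Section IV.B lists among its exclusions "Pregnant (as analyzed by a urine pregnancy test". The footnotes to both tables carry the same sentence: "A urine pregnancy test will be administered at Week 0 to determine eligibility". No other test is dated anywhere in the document.

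**What the exclusion guards.** In the nutrition module (III.A), participants, guided by their therapist, "will determine a daily goal for caloric intake to assist in identifying healthy and realistic weekly weight loss goal". The exercise module (III.B) aims at 30 minutes on 5 days a week.

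**The concern.** The optional waitlist course was added to the schedule but not carried through to two related places.

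First, the risk section gives one scan count and one dose for everybody, and neither fits the patients who take the option. A protocol that chooses to state a number should state the right one for each group.

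Second, the pregnancy test is the plan's stated means of keeping pregnant patients out of a weight-loss and exercise programme that includes X-ray scans. In the NEW Tx arm that programme starts about one week after the test. For waitlist patients the footnote points to a week before their table begins. The reader cannot tell whether they are retested before starting NEW Tx. Disclosure and patient safety are at stake, not any estimate or test in the analysis plan.

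**Working it through.** **1. The plan's own figure.** Inputs: two scans, about 16 microSv and 2 days of background (VI.A).
- Dose per scan, assuming equal doses: 16 / 2 = 8 microSv.
- Background rate implied: 16 / 2 = 8 microSv per day.
- Table 1, DXA row: 2 marks, and 2 × 8 = 16 microSv. The stated figure is reproduced.

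Table 1 covers both arms. Its TAU restriction (the dagger) is attached only to the Intent-to-Attend and Food Diaries rows, so TAU patients have both scans.

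**2. Date of the second scan.** In the text as extracted, several Table 1 rows sit one column too far left. The intact CGI-BP row falls at Weeks 0, 10, 20 and 32, while the Vitals row appears at 0, 9, 18 and 20. Corrected for that shift, the second DXA mark is the Week 20 post-treatment visit. The count of two does not depend on this correction.

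**3. Waitlist total.** Table 2 adds one post-treatment mark, which IV.A dates to Week 40.

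| Group | Scans (weeks) | Dose at 8 microSv each | Background days (dose / 8) |
|---|---|---|---|
| NEW Tx arm | 0, 20 | 16 | 2 |
| TAU only | 0, 20 | 16 | 2 |
| TAU, then NEW Tx | 0, 20, 40 | 3 × 8 = 24 | 3 |

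Excess over the stated dose: (24 − 16) / 16 = 50%.

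**4. Which line governs the scans.** Both table footnotes also list DXA under Vitals. Vitals has more marks than the DXA row: four against two in Table 1, and two against one in Table 2. The separate DXA rows are more specific, and the two marks in Table 1 agree with VI.A. They are used here, but the sponsor should confirm them.

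**5. Pregnancy test, two readings of the Table 2 footnote.** Interval = week of the event minus week of the last dated test.

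| Event | Test at study Week 0 (literal) | Test at waitlist entry (Week 20 or 21) |
|---|---|---|
| NEW Tx starts, Week 21 | 21 − 0 = 21 weeks | 0 to 1 week |
| Third scan, Week 40 | 40 − 0 = 40 weeks | 19 to 20 weeks |

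On the literal reading the sentence adds nothing for waitlist patients and leaves them without a new test. On the other reading a test is intended but carries a week that Table 2 does not have. Either way the footnote needs correction.

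**The case against.** The strongest reply is that a retest at waitlist entry was intended. Waitlist patients follow the procedures of the NEW Tx group, which is tested at entry. The test sentence is repeated under a table that applies only to them. Table 2 also marks the URICA and the metabolic cart in its first column, so some entry measures are repeated. This reading is reasonable. A reader might infer that the plan lets pregnant patients start NEW Tx unchecked, but the documents support that only if the footnote is taken literally.

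It does not settle the matter. Section IV.A spells out the shared procedures as assessments at Weeks 30, 40 and 52. Where the authors wanted a safety procedure extended to this group, they dated it: Section IV.B lists the additional waitlist blood draws. The Table 2 footnote was also partly adapted, since the EKG sentence and the timing of height were removed, yet the Week 0 test stayed.

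A second reply is that pregnancy is an entry criterion and nothing promises a test before every scan. This stands. A reader might infer that the absence of tests before the Week 20 scan in the NEW Tx arm and before the Week 40 scan breaks the plan's rules. No text is contradicted there.

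Third, the practical weight is low. The extra dose is about 8 microSv, or one day of background on the protocol's own scale. Section VI.B allows withdrawal when staying in the study poses substantial risk, although that helps only once a pregnancy is known.

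**Conclusion.** The point holds and is minor. By the DXA rows, patients who move from TAU to NEW Tx have three scans, not two, and about 24 microSv, not 16, assuming an equal dose per scan. Their pregnancy test carries a date that cannot be right for their schedule unless no new test is meant. In that case the weight-loss course starts about 21 weeks after the only test.

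The number of patients affected is not known: they come from the TAU arm only, and uptake of the option is not stated. The documents give no basis for an expected number of pregnancies, so none is offered.

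A reader might also infer that participants were misinformed. That cannot be judged, because the consent pages are not part of the documents. The finding is confined to the protocol's risk section and schedules.

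**What to change.** 1. Ask the sponsor to confirm that the DXA rows, and not the Vitals footnotes, set the scan dates. Then remove DXA from the Vitals definition.
2. Add one clause to VI.A: TAU patients who choose NEW Tx have three scans, about 24 microSv in total (about 3 days of background).
3. Replace the Week 0 sentence under Table 2 with a urine pregnancy test at waitlist entry for women who can become pregnant. It can be done at Week 20 before the scan, or at Week 21 before NEW Tx starts. State the consequence of a positive result: no NEW Tx weight-loss course and no further DXA scan.

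As a suggestion only, and not to repair an inconsistency, the same test could be done before the Week 20 scan in the NEW Tx arm and before the Week 40 scan.

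The cost is one urine test per eligible woman who enters the waitlist course, at a visit already scheduled. The optional tests add one each, also at existing visits. A woman with a positive test would lack her later DXA values, but none of the analyses in Section VIII.B uses DXA. No visit, scan or analysis is added.

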- iii. Participants' NEW Tx therapists will be available to them to discuss any concerns throughout the treatment period. The PI, or a covering clinician from the MGH Bipolar Clinic and Research Program, will make every effort to be available at all times to study participants in the event of a clinical emergency. However, if immediate assistance is required, the participant will be directed call 911 or go to the MGH Acute Psychiatric Service which is open and staffed 7 days a week, 24 hours a day. Participants will be withdrawn from either the open trial (Phase I) or the pilot study (Phase II) if their clinical condition deteriorates substantially. Participants may also be withdrawn if, in the judgment of the study investigators, remaining in the study poses a substantial risk to the participant or a higher level of care is needed.

C. Ensuring Confidentiality

To ensure protection of confidential information, all data will be coded and stored in locked files in the MGH Bipolar Clinic and Research Program. Names will not be included in computerized data files or in any published reports. Case records will be reviewed only by study personnel or, if necessary, by institutional, state, or federal regulatory personnel. All research personnel will have completed the Collaborative Institutional Training Initiative (CITI) Program on-line training and final exam, be well versed in Health Insurance Portability and Accountability Act (HIPAA) regulations and procedures, and be approved as study staff by the IRB. All HIPAA guidelines will be followed and all research personnel will be educated about the importance of strictly protecting participants' rights to confidentiality.

VII. DATA COLLECTION

All data collection will adhere to HIPAA regulations. Data will be obtained specifically for research purposes and managed using the REDCap system. Data on feasibility and satisfaction of NEW Tx as well as medical burden, BD symptoms, and functioning will be collected via patient self-report, clinician- and rater-administered assessments. These data will be used to evaluate treatment feasibility and acceptability, treatment integrity, efficacy, and possible mechanisms of change. Data assessing safety and adverse events will be collected through blood analysis.

A. Safety and Monitoring

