There will be a Data Safety and Monitoring Board (DSMB) for this study composed of three investigators who have experience in clinical research, clinical treatment of BD, and specifically overseeing the safety of participants in bipolar trials. This DSMB will monitor safety issues, including the review of adverse events, the PI's quarterly report of the study's progress, all IRB amendments, the adequacy and integrity of accumulating data, and the capability of the Phase I and II trials to test the hypotheses. The purpose of this process is to assess scientific integrity and patient safety issues, and ensure the ethical conduct of the trials. The DSMB will approve the initiation of the study and subject enrollment, and determine if study procedures should be altered or stopped due to evidence of benefit or harm to trial subjects that may be attributable to NEW Tx or reasons related to scientific integrity. The PI will submit quarterly reports to the DSMB detailing any study changes, adverse events, subject recruitment and retention, reasons for early termination, and ongoing data reports. The PI will also respond to all DSMB issues and queries.

B. Adverse Events

Any serious adverse events (e.g., death, suicide attempt, hospitalization) will be reported within 24 hours to the IRB and the NIMH program officer. A full written report of the event will be sent to the above entities within 10 working days of the event's occurrence. All adverse events will be assessed for the events' severity/intensity, expectedness, relatedness to NEW Tx, clinical outcome, and any action taken due to the event. Any adverse event (e.g., causing interference with usual activities or requiring treatment) and which appears definitely, probably, or possibly related to study participation will be tracked and reported to the IRB at the yearly continuing review. Any serious adverse events will be summarized in the NIMH, DSMB, and IRB annual progress reports. We will also inform the NIMH, DSMB and the IRB of actions, if any, as a result of their continuing review.

VIII. DATA ANALYSIS

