Baseline demographic and clinical characteristics will be examined by the PI in collaboration with [name]., Professor of Biostatistics. Measures of central tendency and variability will be estimated on each continuous measure; proportions estimated for categorical variables. Transformations will be used when distributional assumptions are not fulfilled for inferential tests. Dropouts and completers will be compared on baseline variables using Mann-Whitney or chi-square tests.

A. Data Management: REDCap

To ensure the quality of electronic data capture (EDC) and management, the data management team will use the REDCap EDC system. The REDCap Consortium is comprised of 135 active institutional partners and it supports two secure, web-based applications (REDCap and REDCap Survey) designed to support data capture for research studies. The REDCap application is currently in production use or development build-status for more than 2990 studies with over 9540 end-users spanning numerous research focus areas across the consortium, and the REDCap Survey application is now being adopted rapidly by consortium partners. Both REDCap and REDCap Survey provide a process for building a database or online survey, an interface for collecting data, data validation, and automated export procedures for data downloads to statistical packages (SPSS, SAS, Stata, R).

REDCap allows users to design and implement study scales to collect, store, retrieve, and manipulate data electronically. The REDCap platform for EDC that streamlines data collection and management, and the system is a study management tool used to monitor visit timing and completion in real-time, thus helping to minimize missing data. REDCap is already used at MGH for treatment studies and has proved extremely useful for conducting and managing studies. It obviates the need for data entry by staff, thus minimizing cost and human error. Furthermore, because data quality control checks can be built into the logic of the online measures, problems can be identified in real-time, thereby improving data quality and consistency.

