- iii. **Aim 3: Exploratory Aims (Phase II).** *Hypotheses 3a and 3b:* Between treatment group effects sizes (and 95% CI) will be calculated. To supplement this, Mann-Whitney tests will compare treatment groups on medical burden (as measured by FRS) (*Hypothesis 3a*) and on improvement in symptoms (MADRS, YMRS) and functioning (LIFE-RIFT) (*Hypothesis 3b*) based on change from baseline. *Hypothesis 3c.1:* We will investigate baseline BMI as a potential moderator of treatment response. The focus will be on the magnitude of the effect, not on significance testing. The between treatment group effect sizes (i.e., FRS, MADRS, YMRS, LIFE-RIFT) will be compared with those who have high baseline BMI (> 30) versus low BMI (< 30). *Hypothesis 3c.2:* Mastery of the diet (Nutrition Data System score of food diaries) and exercise (weekly exercise duration from Exercise Questionnaire) modules will mediate the association of NEW Tx and improvement in medical burden (FRS). The

dependent variable will represent change in the FRS score from time of completion of respective module. The mediators will be tested separately. Differential between treatment group effect sizes for those who did and did not master the modules will provide evidence of a mediator of treatment.

C. Rate of Attrition

Some attrition (i.e., 20%) is expected and this can result in bias and reduce power, precision and generalizability⁷⁹. Consistent with the Intent to Treat principle⁸⁰, we will continue with the assessments for the study duration, even among those who fail to comply with the treatment⁸¹. As one aspect of the feasibility study, we will assess the likelihood to attrite using the “Intent to Attend” measure⁷².

D. Power Analysis

The sample sizes for the Phase I and II trials are based primarily on the fundamental aim of this project: feasibility. The N is not based on what is needed for inferential analyses as they are not a fundamental aspect of the design. Power analyses are not indicated for the proposed exploratory analyses. We acknowledge that we will not have sufficient power to detect large effects (e.g., $d = .80$).

IX. REFERENCES

1. Hennekens C. Increasing global burden of cardiovascular disease in general populations and patients with schizophrenia. *Journal of Clinical Psychiatry*. 2007;68(suppl 4):4-7.

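### The rule that withdraws deteriorating patients from the trial conflicts with the intent-to-treat promise to keep assessing them, and could modestly bias the exploratory effect sizes

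*Combined protocol and SAP*

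**What the plan says.** Section VI.B, item iii, sets a mandatory rule: "Participants will be withdrawn from either the open trial (Phase I) or the pilot study (Phase II) if their clinical condition deteriorates substantially". No scale or threshold defines substantial deterioration. The next sentence lets investigators also withdraw anyone for whom staying in poses serious risk or who needs more intensive care. Both sentences concern leaving the study, not leaving NEW Tx. Item i of the same section adds: "If withdrawal from the study is necessary, we will provide appropriate referrals for other treatment".

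Section VIII.C expects 20% attrition, notes that it can cause bias, and invokes intent to treat: "we will continue with the assessments for the study duration, even among those who fail to comply with the treatment".

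Three other provisions bear on patients who leave:
- Table 1 heads the Week 20 column Post/ET, with the footnote "ET= Early Termination".
- The opening of Section VIII states: "Dropouts and completers will be compared on baseline variables using Mann-Whitney or chi-square tests".
- Section IV.C, item xvi, collects Intent to Attend, to be "used in part to inform the extent to which attrition is ignorable".

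Section VIII.B, item iii, compares the arms on change from baseline by effect sizes with 95% CIs, supplemented by Mann-Whitney tests: FRS for hypothesis 3a, and MADRS, YMRS and LIFE-RIFT for 3b. It gives no rule for a missing Week 20 score and no place for an ET score.

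**The concern.** The trigger for withdrawal, clinical worsening, is close to what MADRS, YMRS and LIFE-RIFT measure. If leaving the trial means no further ratings, the scores most likely to be poor go missing because they are poor. Under a common rule, an effective treatment would also make this happen more often in TAU than in NEW Tx.

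The attrition provisions do not reach this case. A baseline comparison of dropouts and completers cannot show worsening after baseline. Intent to Attend records the patient's own intention, not an exit imposed by staff. No adjusted analysis is specified.

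This matters because Section IV.A, item ii, gives Phase II the purpose "to further examine feasibility, to estimate an effect size, and to explore its efficacy for reducing medical burden". The estimates at stake are the exploratory 3b effect sizes, and the 3a effect size for FRS if the Week 20 lipids or blood pressure are lost.

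**Working it through.** **Reading the text.** A non-complier, the group Section VIII.C names, has stopped treatment but is still in the study. A patient under Section VI.B, item iii, has left it. One sentence promises ratings to the end and the other ends participation, so staff facing a deteriorating patient could defend either course. What could be lost for hypotheses 3a and 3b is the Week 20 score, and Week 10 too if withdrawal comes before it.

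**Illustration.** The documents give no withdrawal rate, threshold, correlation or design effect size, so there is no planned figure to reproduce. Everything below is assumed except the sample sizes.

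- X is the state at exit and Y the Week 20 change score. Higher is worse, within-arm SD is 1, and the correlation is ρ.
- TAU: X and Y have mean 0. NEW Tx: Y has mean −0.50 (true d = 0.50), and X has mean −0.50 (full effect at exit) or −0.25 (half).
- In both arms a patient is withdrawn if X > c, with c set so that 10% or 20% of TAU is withdrawn.
- For each arm, a = c − mean(X), p = 1 − Φ(a), and φ is the normal density at a.

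*Observed cases only.* Mean = mean(Y) − ρφ/(1−p). Variance = 1 − ρ²(aλ + λ²), with λ = φ/(1−p).

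*ET score in place of Week 20.* Mean = mean(Y) + p[mean(X) − mean(Y)] + (1−ρ)φ. The SD comes from the second moments of the same mixture.

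Worked case, 10% of TAU withdrawn and full effect at exit: c = 1.2816.
- TAU: p = 0.100, φ = 0.1755.
- NEW Tx: a = 1.7816, p = 0.0374, φ = 0.0816. Of 30 per arm, that is about 3.0 TAU and 1.1 NEW Tx patients.
- Observed cases: difference = 0.50 − ρ(0.1755/0.90 − 0.0816/0.9626) = 0.50 − 0.110ρ. At ρ = 0.5, 0.445/0.97 = 0.46. At ρ = 1, 0.390/0.88 = 0.44.
- ET score: difference = 0.50 + (1−ρ)(0.1755 − 0.0816). At ρ = 0, 0.594/1.08 = 0.55. At ρ = 0.5, 0.547/1.065 = 0.51. At ρ = 1, 0.50.

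Estimated d when the true d is 0.50:

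| TAU withdrawn | Effect at exit | NEW Tx withdrawn | Observed cases, ρ = 0.5 / 1 | ET used, ρ = 0 / 0.5 / 1 |
|---|---|---|---|---|
| 10% | 0.50 | 3.7% | 0.46 / 0.44 | 0.55 / 0.51 / 0.50 |
| 10% | 0.25 | 6.3% | 0.48 / 0.51 | 0.49 / 0.47 / 0.48 |
| 20% | 0.50 | 9.0% | 0.43 / 0.41 | 0.57 / 0.52 / 0.50 |
| 20% | 0.25 | about 14% | 0.48 / 0.51 | 0.47 / 0.45 / 0.45 |

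If less than half the effect is present at exit, the range widens. With none present and 10% withdrawn in each arm, observed cases give 0.52 to 0.59 (ρ = 0.5 to 1) and ET scores give 0.40 to 0.43 (ρ = 0 to 1).

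*No true effect, same rule in both arms.* p and φ are equal, so every difference is 0.

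*FRS.* The same formulas apply, but ρ between clinical state at exit and FRS change is unknown. At ρ = 0 the observed-case difference is exactly 0.50, so the loss would then be of numbers rather than a bias.

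*Scale.* Standard error of d is about √(2/30) = 0.26 with 60 randomized (Sections IV.A and IV.B) and √(2/20) = 0.32 with 40 (Section II). The largest tabulated shift is about 0.06 at 10% and 0.09 at 20%, so 0.06/0.26 = 0.23 and 0.09/0.26 = 0.35 of a standard error.

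**The case against.** **Section VIII.C already covers these patients.** Its wording extends a general commitment to a hard case and does not confine it to non-compliers. Section VI.B is a list of patient protections, where silence about ratings proves little. This is the more natural reading of VIII.C, and it rules out an inference a reader might draw: that the plan intends to stop rating patients who get worse. What stands is the conflict, because the VI.B rule is mandatory and operates on study participation.

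**An exit rating is planned.** True, so the deterioration need not go unrecorded. With the full effect present at exit and ρ of 0.5 or more, using ET scores keeps d at 0.50 to 0.52. But the plan does not say that they are used.

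**Little is lost outside the Week 20 comparison.** A reader might infer that all later ratings matter equally. They do not. Week 32 and the waitlist visits fall after the 20-week comparison, and CGI-BP is not an outcome in Section VIII.B.

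**The effect is small and rests on assumptions.** Also true. Hypotheses 3a and 3b are exploratory, and Section VIII.D says the sample size was not set for inference. That limits the weight of the point, but the remedy is a few sentences.

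**Conclusion.** The point holds as an unresolved conflict between two stated rules, with a modest possible bias in exploratory Phase II effect sizes. Under the assumptions shown, a true d of 0.50 is estimated at 0.44 to 0.55 with 10% TAU withdrawal and 0.41 to 0.57 with 20%, if at least half the effect is present at exit. These shifts are well inside the standard error.

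A reader might infer that the bias favours NEW Tx. The documents do not settle the direction: it depends on whether ET scores are used, how much of the effect is present at exit, and whether deterioration is noticed equally in both arms. NEW Tx patients have 18 therapist sessions and so may be noticed more often, but TAU patients also see clinicians, and no detection rates are given.

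A reader might also infer that the primary aims or patient safety are compromised. They are not. Withdrawn patients still count against retention, which Section VIII.B, item ii, defines as completers over randomized. Adverse events are reported under Section VII.B, and the quarterly DSMB reports under Section VII.A cover "reasons for early termination, and ongoing data reports". Phase I has no comparator. This is a cheap improvement.

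**What to change.** - Reword both withdrawal sentences in Section VI.B, item iii (deterioration; serious risk or need for more care), so that they stop NEW Tx where it is being given and trigger referral in both arms, but do not end follow-up. Changing only the first would leave the second as a route out for the same patients.
- State that the Section VIII.C commitment applies to these patients: assessments already scheduled, above all Week 20, continue in both arms unless consent is withdrawn or assessment is clinically inappropriate.
- If a visit must be shortened, give priority to the clinician ratings (MADRS, YMRS, LIFE-RIFT). Keep blood pressure and the lipid draw where feasible, so that FRS can be calculated.
- In Section VIII.B, item iii, state that an observed Week 20 score takes precedence over an ET score, and that the ET score is used only in a sensitivity analysis when Week 20 is missing.

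The cost is protocol wording; no visits are added. The downside is that some visits will be missed, rearranged or shortened, and staff must judge when an acutely ill patient can be rated.
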